1. DOMAIN SUMMARY

1.1. Domain Summary

Strata	Myeloma, Non-Hodgkin Lymphoma and Chronic Lymphocytic Leukaemia
Domain-specific inclusion criteria	None.
Domain-specific exclusion criteria	
Exclusion Criteria
 
Patients will not be eligible for this domain if they fulfil any of the following criteria:
 
 1. Prior or planned allogeneic haematopoietic stem cell transplantation. 2. Already receiving systemic antibiotic prophylaxis for the purpose of preventing bacterial infection (NB: patients may receive antiviral, antifungal and PJP prophylaxis). 3. Received immunoglobulin replacement in the preceding three months. 4. Objection to receiving immunoglobulin products. 5. Known history of IgA deficiency with anti-IgA. 6. History of severe allergy to immunoglobulin products. 7. Current active infection requiring systemic antibiotics. 8. Allergy or intolerance of all domain antibiotic options. 9. Pregnant or breastfeeding. 10. Severe renal impairment (estimated or measured creatinine clearance of < 30 mL/min). 11. Previous splenectomy. 12. Previous participation in this domain. 13. Treating team deems enrolment in the domain is not in the best interest of the patient.
Interventions to be compared	
Arm A: Start prophylactic oral antibiotics: Once daily trimethoprim-sulfamethoxazole (co-trimoxazole) 160mg/800mg.
 
NB: Doxycycline 100mg daily as an alternative for patients with hypersensitivity to co-trimoxazole.
 
Arm B: Start immunoglobulin replacement IVIg every 4 weeks \pm 1 week at a dose of 0.4g/kg, modified to achieve an IgG trough level of at least lower limit of age-specific serum IgG reference range; or SC Ig, weekly, may be used in patients who meet local criteria for home-based self-administration in centres with established SC Ig programs. Dosing is usually given at 100mg/kg/week, modified to achieve an IgG steady state level of at least the lower limit of the serum reference range. A loading IVIg dose may be given in the first month if required.
 
Planned treatment duration for all arms (A and B) is 12 months.

Trial hypotheses	1. Prophylactic oral antibiotics are non-inferior to Ig replacement for the prevention of severe, and/or recurrent infection in patients with secondary hypogammaglobulinaemia due to B-cell malignancies.
Primary outcome measure	Primary RATIONAL-PT Endpoint: refer to RATIONAL-PT Core Protocol
Secondary outcome measures	Secondary RATIONAL-PT Endpoints: refer to the RATIONAL-PT Core Protocol.

2. PROTOCOL APPENDIX STRUCTURE

The structure of the RATIONAL Platform Trial protocol is different to that used for conventional trials because this trial is adaptive and the description of these adaptations is better understood and specified using a ‘modular’ protocol design.

The protocol has multiple modules, in brief, comprising a Core Protocol (overview and design features of the study); a Master Statistical Analysis Appendix (details of the current statistical analysis plan and models); Domain-Specific Appendices (DSA) (detailing all interventions currently being studied in each domain); and Region-Specific Appendices (RSA) (detailing regional management and governance).

The Core Protocol contains all information that is generic to the trial, irrespective of the regional location in which the trial is conducted and the domains or interventions that are being tested.

The DSA contains information about the intervention(s), within each domain, because one of the trial adaptations is that domains and interventions will change over time. These Appendices are anticipated to change over time, and each modification to a DSA will be subject to a separate ethics application for approval.

Information that is specific to a particular region in which the trial is conducted is contained within a RSA. This includes information related to local management, governance, and ethical and regulatory aspects. Within each region, only that region’s RSA, and any subsequent modifications, will be submitted for ethical review in that region.

In addition to the Master Statistical Analysis Appendix, a Domain-Specific Statistical Analysis Plan (DSSAP) will be prepared that will outline additional aspects of the statistical analysis for this domain.

4. BACKGROUND AND RATIONALE

4.1. Domain definition

This is a domain within the RATIONAL Platform Trial to test the effectiveness and safety of prophylactic antibiotics as an alternative Ig replacement in patients who have not yet commenced Ig replacement therapy.

4.2. Domain-specific background

4.2.1. Overview

4.2.2. Immunoglobulin replacement therapy in acquired hypogammaglobulinemia due to haematological malignancies

Evidence supporting the use of Ig replacement therapy (IgRT) in patients with haematological malignancies is limited. IgRT used to prevent recurrent bacterial infections for patients with MM, NHL & CLL is provided under Australian Criteria for government-funded Ig – with the caveat of “*Evidence of probable benefit – more research needed*”.¹ This recommendation is based on outdated data. Whilst the most recent Cochrane review which showed IgRT reduced infections in patients with secondary hypogammaglobulinemia due to blood cancers, it only included only 3 trials published between 1988 and 1995 with *a total of only 205 patients*.²⁻⁵ In our recently completed systematic review of interventions to prevent infections in CLL, MM and NHL we ***did not identify any new evidence*** to guide Ig use.⁶ We found no difference in risk of all-cause mortality in patients allocated to IgRT compared to standard of care (relative risk 1.35, 95% CI 0.57-3.18), however a reduction in risk of clinically documented infections (RR 0.70, 95% CI 0.54-0.96, see figure 1). However, our certainty in the evidence was low due to small sample size of included trials, classification of infection outcomes, high risk of bias in the included studies and lack of contemporary data applicable to the current standard of care.⁶ These trials did not specify if routine prophylactic antibiotics were administered. Since these trials, there have been major changes to cancer therapy and supportive care. Intensive and novel therapies have improved outcomes for patients who respond, with varying degrees of immunological recovery. Therefore, it is very uncertain as to whether results from these early trials of IgRT still apply to our current practice. We have no current data to inform which patients should receive IgRT. This lack of evidence has led to substantial variation to the use of IgRT, both internationally and within Australia.⁷

[figure not shown]
Figure 1. Immunoglobulin replacement vs standard of care on one or more clinically documented infection

4.2.3. Prophylactic antibiotics as an alternative to immunoglobulin replacement

Short-term prophylactic oral antibiotics have been shown to reduce infections by 30-50% in neutropenic haematology patients following chemotherapy,⁸ and in non-haematologic patients with bronchiectasis,⁹ supporting the rationale for their use in acquired hypogammaglobulinaemia. A recent systematic review of prophylactic antibiotics in MM showed infection reduction in the first 3 months after diagnosis, but no mortality difference.¹⁰ Our systematic review identified 4 trials of prophylactic antibiotics in patients with MM, and although antibiotics did not reduce all-cause mortality (RR 1.11, 95% CI 0.85-1.45) or infection in our review (RR 0.84, 95% CI 0.34-2.09, Figure 2), the included studies did not specify whether patients had hypogammaglobulinaemia or whether they were also receiving IgRT.

Figure 2. Prophylactic antibiotics vs standard care on one or more clinically documented infections

Despite the limited evidence for their use, some international guidelines recommend a trial of prophylactic antibiotics prior to commencing IgRT,¹¹ but this is not required in Australia or other jurisdictions. Potential advantages of antibiotics include reduced total healthcare costs, possible improvements to QoL with fewer hospital attendances for infusions, and reduction in Ig adverse effects. On the other hand, antibiotic resistance is a concern with wider use of prophylactic antibiotics.^{9,12} Antibiotics also have different safety profiles to IgRT. Therefore, the use of prophylactic antibiotics should be properly evaluated with respect to efficacy, safety, QoL, and healthcare costs.

4.2.4. Comparison of IgRT with prophylactic antibiotics

[figure not shown]
In our systematic review, the only

trial that we identified that

directly compared starting prophylactic antibiotics with starting IgRT in patients with acquired hypogammaglobulinemia was our recently completed the RATIONAL phase II feasibility trial (ACTRN12616001723471). This trial compared the use of IgRT vs prophylactic oral antibiotics in 63 patients with CLL, MM & NHL.

RATIONAL demonstrated recruitment feasibility and tolerability of oral antibiotics. Although not powered for clinical outcomes, RATIONAL data suggested that infection rates were not increased in the antibiotic arm (the lower quartile for time to first major infection was 11.1 months in the immunoglobulin and 9.7 months in the antibiotic arm Figure 3).¹³ Clinically documented infections averaged 1.86 per participant in the immunoglobulin treatment arm and 1.33 per participant in the prophylactic antibiotic treatment arm. As this was a feasibility study, our results need to be confirmed in a larger trial.

Figure 3: Time to first major (grade 3+) infection

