9. DOMAIN ENDPOINTS

The Start Ig domain aims to demonstrate the efficacy and safety of prophylactic antibiotics compared to IgRT in adults with a diagnosis of MM, CLL or NHL who are eligible to receive immunoglobulin replacement for recurrent or severe infections or an IgG <4g/L (excluding paraprotein).

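### Does citing an earlier major-infection quartile on antibiotics as evidence of no increase undermine the non-inferiority comparison?

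*Protocol*

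**What the plan says.** Section 4.2.4 describes the pilot, the only direct comparison that the sponsor's systematic review found. Its reading, given with the caveat that the pilot lacked power for clinical outcomes, is: "infection rates were not increased in the antibiotic arm (the lower quartile for time to first major infection was 11.1 months in the immunoglobulin and". The antibiotic figure that completes the bracket is 9.7 months. The next sentence turns to all clinically documented infections: "Clinically documented infections averaged 1.86 per participant in the immunoglobulin treatment arm", against 1.33 on antibiotics. The paragraph ends by saying that a larger trial must confirm the results.

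Section 4.2.2 gives the effect of immunoglobulin replacement (IgRT) against standard of care as "a reduction in risk of clinically documented infections (RR 0.70, 95% CI 0.54-0.96"). It rates the certainty as low and adds that "it is very uncertain as to whether results from these early trials of IgRT still apply to our current practice". Section 4.2.3 gives antibiotics against standard care as RR 0.84 (0.34 to 2.09) for infection, from trials in myeloma.

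Sections 1.1, 4.3.1 and 6 state a non-inferiority hypothesis. Section 5.1 sets the aim as effectiveness relative to IgRT on event-free survival, as defined in the Core Protocol. Section 9 opens: "The Start Ig domain aims to demonstrate the efficacy and safety of prophylactic antibiotics compared to IgRT in adults". Section 8.1.1 lists two active arms and no untreated arm. Section 12 leaves all statistical matters to the Master Statistical Analysis Appendix and the domain-specific analysis plan.

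**The concern.** Three things catch the eye.

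- **The pilot.** The text claims no increase in infection on antibiotics and cites a time to major infection that is shorter on antibiotics. The hypothesis covers severe infection, so this is the more relevant of the two pilot results. If a power calculation assumed equal hazards on the strength of this sentence, it would be optimistic.
- **The control effect.** The interval 0.54 to 0.96 is not centred on 0.70 on the log scale, so one of the three printed numbers may be wrong. A non-inferiority margin would normally draw on the limit nearest 1.
- **The aim.** Section 9 speaks of demonstrating efficacy. With no untreated arm, and a comparator whose benefit could be as small as 1 − 0.96 = 4%, non-inferiority alone would not show that antibiotics beat no prophylaxis.

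At stake would be the credibility of the sample size and of the trial's main conclusion.

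**Working it through.** The document states no sample size, margin, alpha or power, so there is no design figure to reproduce. What can be checked is how much the quoted background figures carry.

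**1. Quartiles (section 4.2.4).** With exponential times, HR = lower quartile on IgRT / lower quartile on antibiotics = 11.1/9.7 = 1.144. With Weibull shape k, HR = 1.144^k, which is 1.07 for k = 0.5 and 1.31 for k = 2. The implied 12-month risks are:

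- IgRT: 1 − 0.75^(12/11.1) = 26.7%
- antibiotics: 1 − 0.75^(12/9.7) = 29.9%

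These agree roughly with the 25% or so quoted in section 4.2.7.

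**2. Precision of that ratio.** Events ≈ 0.25 × 63 = 15.75. Assuming equal arms (arm sizes are not given), SE(log HR) ≈ 2/√15.75 = 0.504. The 95% interval is exp(0.135 ± 1.96 × 0.504) = 0.43 to 3.07. With 20% or 30% of patients having an event, it is 0.38 to 3.45 or 0.46 to 2.82. If the true hazards were equal, an estimate of 1.144 or higher would arise about 39% of the time.

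**3. Infection counts (section 4.2.4).** Rate ratio = 1.33/1.86 = 0.715. With 31.5 patients per arm and Poisson counts, SE = √(1/58.6 + 1/41.9) = 0.202, so the 95% interval is 0.48 to 1.06. Doubling the variance for over-dispersion gives 0.41 to 1.25. This result leans towards antibiotics and is also compatible with no difference.

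**4. The relative risk in section 4.2.2.** The log-midpoint of the interval is √(0.54 × 0.96) = 0.720. With both limits at their rounding extremes it runs from √(0.535 × 0.955) = 0.715 to √(0.545 × 0.965) = 0.725, while an RR printed as 0.70 is at most 0.705. Rounding does not close the gap. The other three quoted RRs do reproduce:

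| Printed RR | Log-midpoint |
|---|---|
| 1.35 | √(0.57 × 3.18) = 1.346 |
| 1.11 | √(0.85 × 1.45) = 1.110 |
| 0.84 | √(0.34 × 2.09) = 0.843 |

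If 0.70 and 0.54 are right, the upper limit would be 0.70²/0.54 = 0.91. If 0.70 and 0.96 are right, the lower limit would be 0.70²/0.96 = 0.51.

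**5. Consequences that might be drawn.** A margin set at the quoted upper limit would be 1/0.96 = 1.04. With one-sided alpha 0.025, 80% power and true HR 1, that needs 4 × (1.96 + 0.8416)²/ln(1/0.96)² ≈ 18,840 events. At the point estimate the margin would be 1/0.70 = 1.43 and the need 247 events. A trial with 80% power at HR 1.0 would have about 28%, 46% or 62% power at HR 1.14 for assumed margins of 1.3, 1.5 or 2.0. None of these margins is in the document. They also carry a risk ratio for one or more documented infections, or a hazard ratio for grade 3+ infection, over to event-free survival, whose definition lies in the Core Protocol.

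**The case for a change.** The strongest case for a change is that the bracketed quartiles have the opposite sign from the sentence they support. Data this imprecise cannot support a statement of no increase any more than one of increase, and this is the only head-to-head evidence cited. The asymmetry in the RR interval is not a rounding effect, and a transcription slip is the natural first explanation. Section 9 could be read as promising more than a non-inferiority comparison without an untreated arm can give.

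The first two observations stand as descriptions of the text. The paragraph in 4.2.4 would be more accurate if it said that the major-infection quartile came earlier on antibiotics, that documented infections were fewer, and that both results are imprecise. The RR and its interval merit a check against the source, although an interval method that is not symmetric on the log scale would also explain the gap.

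The third does not stand. Section 9 qualifies efficacy as relative to IgRT, and sections 1.1, 4.3.1 and 6 name non-inferiority outright. No superiority over no prophylaxis is claimed, and section 4.2.2 is open about how weak and dated the IgRT evidence is. The 4% is one end of an interval whose point estimate is a 30% reduction and whose other end is 46%. The power argument criticises a statement that this document does not make.

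**Conclusion.** No change to the plan follows. Two small flaws in the background are real: a bracket in 4.2.4 that sits badly with its sentence (9.7 against 11.1 months), and an RR in 4.2.2 whose interval centres on 0.72 rather than 0.70. Both are clerical, fit for tidying whenever the text is next opened.

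The hazard ratio of 1.14 is derived from one point on each curve under constant hazards and was not reported by the pilot. Its interval of about 0.43 to 3.07 gives no basis for re-planning, and writing it into the protocol would lend it a precision that it lacks. Nothing in this document takes either figure as an input: eligibility, arms, endpoints, follow-up and subgroups would be the same if both sentences were rewritten.

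This rests on three assumptions: roughly equal pilot arms, about 25% of pilot patients with a grade 3+ infection, and margin and sample size being set and justified in the Core Protocol's statistical appendix and the domain analysis plan, as section 12 says. Whether those documents justify their margin and control effect well is a question for them and cannot be settled from this text.

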4.2.5. Potential risks of Ig therapy

Regular IgRT is associated with hospital day-admissions (for intravenous administration) and known adverse effects associated with Ig use. Common adverse effects include headache, lethargy, nausea/vomiting, allergic reactions, arthralgia, myalgia, hypersensitivity reactions, abdominal pain

and dyspnoea. Aseptic meningitis can also occur, although this is less common. Regular use of Ig has also been associated with risk of thromboembolic events.¹⁴ Renal impairment and renal failure have also been reported in patients receiving IVIg. In patients receiving subcutaneous Ig (SC Ig), there may also be injection site irritation and there is a requirement for training and equipment to self-administer the product. Reduction in use of Ig may help reduce healthcare expenditure on Ig product costs and associated healthcare administration costs.

4.2.6. Potential risks of prophylactic antibiotic therapy

Some common adverse events to the prophylactic antibiotics used within this protocol include nausea, vomiting, diarrhoea and rash. Other less common adverse reactions include anaphylaxis and hypersensitivity reactions. Another possible risk of prophylactic antibiotics is development of resistant organisms, but its impact on development of infection is unknown.

4.2.7. Summary

Secondary hypogammaglobulinemia is common in patients with haematological malignancies and associated with infections (approximately 25% of participants in our pilot trial experienced at least one grade 3 or higher infection). Substantial variation exists in the approach to use of IgRT and alternative therapies such as prophylactic antibiotics in patients with acquired hypogammaglobulinaemia secondary to haematological malignancies, both internationally and within Australia.^{7,15}

4.3. The need for a trial comparing IgRT with prophylactic antibiotics

Our current treatment decisions on whether to use IgRT or prophylactic antibiotics in patients with acquired hypogammaglobulinaemia secondary to haematological malignancies are not evidence-based because there is limited data on efficacy of IgRT or prophylactic antibiotics, and the available trial evidence is limited by small patient numbers, risk of bias and lack of contemporaneous and comparative data. These have been identified as priority evidence gaps in the recent Australian Medical Services Advisory Committee review of the cost-effectiveness of IgRT, specifically:

- Consideration for eligibility criteria used in Europe (trial of antibiotics before starting Ig therapy)
- Cost effectiveness of Ig in NHL (the largest patient group), as there are no Ig studies in these patients.

Therefore, a clinical trial is required to evaluate the comparative efficacy, safety and cost-effectiveness of prophylactic antibiotics compared with IgRT.

4.3.1. Domain hypothesis

Prophylactic oral antibiotics are non-inferior to IgRT replacement for the prevention of severe, and/or recurrent infection in patients with secondary hypogammaglobulinaemia due to B-cell malignancies.

5. DOMAIN OBJECTIVES

5.1. Aims

The aim of this domain is to determine the effectiveness of prophylactic antibiotics compared to IgRT in patients with haematological malignancies and acquired hypogammaglobulinaemia on event-free survival (as defined in the core protocol).

6. DOMAIN DESIGN

This RATIONAL Platform Trial is an investigator-initiated open-label, randomised controlled adaptive platform trial open in multiple sites. The platform design allows many treatment approaches to be tested simultaneously on different patient subpopulations, within the same framework, and for pre-specified interim analyses that can be used to stop recruitment early to arms showing insufficient evidence of efficacy or overwhelming evidence of efficacy. The platform allows the addition of new domains via protocol amendments and DSAs to answer new questions of interest, including different treatments or patient groups. Details of the overall platform trial design are included in the Core Protocol.

The Start Ig DSA is one of multiple domains in the RATIONAL Platform trial. This domain is testing whether commencing prophylactic antibiotics is non-inferior to the standard dose of IgRT in patients with secondary hypogammaglobulinemia due to haematological malignancies.

7. SELECTION AND WITHDRAWAL OF PARTICIPANTS

7.1. Population

The RATIONAL Platform Trial enrolls patients with acquired hypogammaglobulinemia due to haematological malignancies, including multiple myeloma [MM], chronic lymphocytic leukaemia [CLL] and non-Hodgkin lymphoma [NHL]. This domain is available for patients who are not currently receiving IgRT for prevention of bacterial infections due to hypogammaglobulinaemia.

7.2. Eligibility criteria

Patients are eligible for the RATIONAL Platform Trial if they meet all of the platform-level inclusion and none of the platform-level exclusion criteria outlined in the Core Protocol. Patients eligible for the RATIONAL Platform Trial may have conditions that exclude them from this Domain.

7.2.1. Domain inclusion criteria

None.

7.2.2. Domain exclusion criteria

1. Prior or planned allogeneic haematopoietic stem cell transplantation.
2. Already receiving systemic antibiotic prophylaxis for the purpose of preventing bacterial infection (NB: patients may receive antiviral, antifungal and PJP prophylaxis).
3. Received immunoglobulin replacement in the preceding three months.
4. Objection to receiving immunoglobulin products.
5. Known history of IgA deficiency with anti-IgA.
6. History of severe allergy to immunoglobulin products.
7. Current active infection requiring systemic antibiotics.
8. Allergy or intolerance of all domain antibiotic options.
9. Pregnant or breastfeeding.
10. Severe renal impairment (estimated or measured creatinine clearance of < 30 mL/min).
11. Previous splenectomy.
12. Previous participation in this domain.
13. Treating team deems enrolment in the domain is not in the best interest of the patient.

7.2.3. Intervention exclusion criteria

Nil

7.3. Randomisation

Randomisation will occur following confirmation of participant eligibility for the domain, between the baseline and Start Domain Day 1 visit. Randomisation will be conducted through a password-protected secure website using a central randomisation programme. Eligibility for randomisation will be assessed with reference to the Platform-level and Domain-level inclusion and exclusion criteria and there will be no exception to eligibility requirements at the time of randomisation.

